 - If ARV regimen is changed ≥ 45 days prior to Pre-Baseline/Day -13, plasma HIV-1 RNA < 50 copies/mL at Pre-baseline/Day -13 visit is required.
- No documented history of resistance to any components of the current ARV regimen
- Availability of a fully active alternative ARV regimen, in the opinion of the Investigator, in the event of discontinuation of the current ARV regimen with development of resistance.
- Hgb ≥ 11.5 g/dL (males) or ≥ 11 g/dL (females)
- WBC ≥ 4000 cells/ μ L
- Platelets $\geq 150,000$ /mL
- ANC ≥ 1500 cells/ μ L
- CD4 count ≥ 400 cells/ μ L
- Albumin ≥ 3.9 g/dL
- ALT and AST $\leq 2 \times$ ULN
- Estimated glomerular filtration rate ≥ 60 mL/min
- No autoimmune disease (e.g. lupus erythematosus, rheumatoid arthritis, inflammatory bowel disease, sarcoidosis, moderate or severe psoriasis)
- No evidence of current HBV infection
 - Positive anti-HBs antibody and negative HBsAg results are acceptable

- No evidence of current HCV infection
 - Positive anti-HCV antibody and negative HCV PCR results are acceptable
- No documented history of pre-ART CD4 nadir < 200 cells/μL
 - Unknown pre-ART CD4 nadir is acceptable
- No history of Class C AIDS-Defining Condition
 - No acute febrile illness within 35 days prior to Pre-Baseline/Day -13

Study Visits and
Procedures:

Visit Schedule:

The main study phase consists of a screening period of up to 35 days, a pre-treatment period of 14 Days (from Day -13 to Day 1), treatment period of 71 days (Cohorts 1 to 3), 127 days (Cohorts 4 to 6), CCI and a follow-up period of 30 days after the last dose of study drug is taken. Enrolled subjects will undergo the following scheduled study visits:

Cohort 1 to Cohort 3

Day -13 (**Pre-Baseline**)

Day 1 (**Baseline/Dose 1**), Day 3, Day 5, Day 8, Day 11

Day 15 (**Dose 2**), Day 17, Day 19, Day 22, Day 25

Day 29 (**Dose 3**), Day 31, Day 33, Day 36, Day 39

Day 43 (**Dose 4**), Day 45, Day 47, Day 50, Day 53

Day 57 (**Dose 5**), Day 59, Day 61, Day 64, Day 67

Day 71 (**Dose 6**), Day 73, Day 75, Day 78, Day 81

Day 101 (**End of Study**)

Cohort 4

Day -13 (**Pre-Baseline**)

Day 1 (**Baseline/Dose 1**), Day 2, Day 3, Day 8

Day 15 (**Dose 2**), Day 22

Day 29 (**Dose 3**), Day 36

Day 43 (**Dose 4**), Day 50

Day 57 (**Dose 5**), Day 58, Day 59, Day 64

Day 71 (**Dose 6**), Day 78

Day 85 (**Dose 7**), Day 92

Day 99 (**Dose 8**), Day 106
Day 113 (**Dose 9**), Day 120
Day 127 (**Dose 10**), Day 128, Day 129, Day 134
Day 157 (**End of Study**)

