Cohorts 5 to 9

Day -13 (**Pre-Baseline**)
Day 1 (**Baseline/Dose 1**), Day 2, Day 3, Day 8
Day 15 (**Dose 2**), Day 22
Day 29 (**Dose 3**), Day 31, Day 36
Day 43 (**Dose 4**), Day 45, Day 50
Day 57 (**Dose 5**), Day 58, Day 59, Day 64
Day 71 (**Dose 6**), Day 73, Day 78
Day 85 (**Dose 7**), Day 87, Day 92
Day 99 (**Dose 8**), Day 101, Day 106
Day 113 (**Dose 9**), Day 115, Day 120
Day 127 (**Dose 10**), Day 128, Day 129, Day 134
Day 157 (**End of Study**)

Subjects who prematurely discontinue study drug will be required to complete an Early Study Drug Discontinuation Visit within 30 days after their last dose of study treatment.

The Pre-Baseline/Day -13 visit has an allowable window of ± 3 days.

- Visits scheduled for 2, 4, 7, or 10 days after a Dosing visit, **except for Day 2, 3, 58, 59, 128 and 129** have an allowable window of ± 1 day.

The Day 101 and 157 visits have an allowable window of ± 3 days.

Non-dosing visits may occur at the investigator site or at other location agreed by the subject and mobile nurse vendor.

Screening Procedures:

Screening procedures include: complete physical examination, vital signs, height, weight, medical history (including route and estimated duration of HIV infection, pre-ART viral set point, and complete ARV history), HIV-1 RNA, ARV trough PK, hematology, serum chemistry, serum pregnancy test, urinalysis, HBV and HCV serologies, eGFR, and electrocardiogram (ECG). Pre-ART CD4 nadir and historical genotype will be collected if available.

In order to establish eligibility, Investigators may repeat screening procedures or laboratory assessments for subjects who have an acute illness or abnormal laboratory value that is expected to resolve without sequelae within the screening window.

On-Study Procedures:

Dosing:

For **Cohorts 1 to 3**, dosing visits will occur at Day 1, Day 15, Day 29, Day 43, Day 57, and Day 71. For **Cohorts 4 to 9**, dosing visits will occur at Day 1, Day 15, Day 29, Day 43, Day 57, Day 71, Day 85, Day 99, Day 113 and Day 127. CCI

For **Cohorts 1 to 4**, subjects will fast for at least 2 hours before dosing. For **Cohorts 5 to 8**, subjects will fast overnight (at least 8 hours) before dosing. CCI

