The Investigator will verify the subject's continued eligibility for dosing at post-Baseline dosing visits, including the absence of dose-limiting toxicities (DLTs) and (for females of childbearing potential) a negative urine pregnancy test, prior to dosing. All doses will be directly administered by blinded site staff. Subjects will fast for 2 hours after dosing for all cohorts. After Dose 1, subjects will remain on site for 12 hours after dosing for safety assessment and phlebotomy.

Safety:

Solicitation of AEs and concomitant medications and symptom-directed physical examination at every visit.

Hematology, serum chemistry, and urinalysis weekly for Cohorts 1 to 3. For **Cohorts 4 to 9** these labs will be collected on dosing days, seven days post dose (starting from Dose 4), at end of study, and ESDD. For **Cohorts 6** CCI these labs will also be collected on Day 2 and two days post dose (starting from Dose 5).

CCI

Urine pregnancy test (for females of childbearing potential) prior to each dose.

Vital signs (blood pressure, pulse, respiration rate and temperature) at all dosing visits.

Subjects will be instructed to contact the site immediately if any flu-like symptoms are noted (eg, fatigue, pyrexia, chills, myalgia, joint pain or headache).

Pharmacokinetics:

Plasma GS-9620 concentrations will be collected at the following time points **for all cohorts**:

- Pre-dose (≤ 5 minutes prior to dosing), 0.5, 1, 2, 4, 6, 8, 10, and 12 hours post dose at Day 1; then one sample 48 hours post dose at Day 3
- **If the SEC approves the dose escalation to 12 mg in Cohort 6, starting from Dose 4 and onwards**, plasma GS-9620 concentrations will also be collected on Day 43 (Dose 4): Pre-dose (≤ 5 minutes prior to dosing), 0.5, 1, 2, 4, 6, 8, 10, and 12 hours post dose; then one sample 48 hours post dose at Day 45

CCI

A single trough ARV PK sample will be collected at Pre-Baseline/Day -13 (**Cohorts 1 to 3**) or at Screening, Day 29, Day 57, Day 85 and Day 99 (**Cohort 5**), or at Screening, Day 57 and Day 99 (**Cohorts 6** CCI CCI

The timing of the ARV trough collection is to be 20-24 hours following the subject's previous QD regimen dose and before next ARV dose (and, for any subject on a regimen containing a BID component, the trough collection must also occur 8-12 hours following the subject's previous dose of that BID component and before next ARV dose). These samples may be analyzed to assess interim ART adherence.

Pharmacodynamics:

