6. STUDY PROCEDURES

The study procedures to be conducted for each subject enrolled in the study are presented in tabular form in [Appendix 2](#) and described in the text that follows.

The investigator must document any deviation from protocol procedures and notify the sponsor or contract research organization (CRO).

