 - 6.4.2.4.2. Hematology profile: complete blood count (CBC) with differential and platelet count (**Days 59 and 129 only**)
 - 6.4.2.4.3. Plasma HIV-1 RNA (TaqMan® v2.0)
 - 6.4.2.4.4. Serum for cytokine/soluble biomarker studies
 - 6.4.2.4.5. Whole blood ISG mRNA panel
 - 6.4.2.4.6. Cell-associated HIV-1 RNA/DNA with stored PBMC
 - 6.4.2.4.7. Plasma HIV-1 RNA Single Copy Assay with stored plasma
 - 6.4.2.4.8. Whole blood for immune cell activation (T, B, NK)
 - 6.4.2.4.9. GS-9620 plasma pharmacokinetic assessment (Day 3 only)

6.4.3. Treatment Assessments on Non Dosing Days 8, 22, 36, 50, 64, 78, 92, 106, 120 and 134

All study visits are to be scheduled relative to the Baseline/Day 1 visit. Study visits on Days 8, 22, 36, 50, 64, 78, 92, 106, 120 and 134 are to be completed within \pm 1 day of the protocol specified visit date. The following procedures will be performed:

- 6.4.3.1. Review of AEs and changes in concomitant medications
- 6.4.3.2. Symptom-directed physical examination as needed
- 6.4.3.3. Urine collection for urinalysis (**Days 50, 64, 78, 92, 120 and 134 only**)

- 6.4.3.4. Blood sample collection for the following laboratory analyses:
 - 6.4.3.4.1. Chemistry profile: alkaline phosphatase, AST, ALT, total bilirubin, direct and indirect bilirubin, total protein, albumin, CPK, bicarbonate, BUN, calcium, chloride, creatinine, glucose, phosphorus, magnesium, potassium, sodium, uric acid **(Days 50, 64, 78, 92, 120 and 134 only)**
 - 6.4.3.4.2. Hematology profile: complete blood count (CBC) with differential and platelet count **(Days 50, 64, 78, 92, 120 and 134 only)**
 - 6.4.3.4.3. Plasma HIV-1 RNA (TaqMan[®] v2.0)
 - 6.4.3.4.4. CD4+ cell count **(Days 50, 64, 78, 92, 120 and 134)**
 - 6.4.3.4.4.1. CD8+ cell count, CD4/CD8 ratio and CD4 % **(Days 50, 64, 78, 92, 120 and 134 for Cohorts 5 to 9 only)**
 - 6.4.3.4.5. Serum for cytokine/soluble biomarker studies **(Days 50, 64 and 134 only)**
 - 6.4.3.4.6. Whole blood ISG mRNA panel **(Days 50, 64 and 134 only)**
- 6.4.4. Treatment Assessments on Dosing Days 15, 29, 43, 57, 71, 85, 99, 113 and 127**

Subjects are to arrive in a fasting state for the Dosing Days 15, 29, 43, 57, 71, 85, 99, 113 and 127 and to follow fasting and food/liquids consumption requirement shown in 1. Initiation of the treatment with the study drug must take place in the clinic and will be administered by blinded study staff.

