6.4.4.9. In-Clinic Dosing

6.4.5. Treatment Assessments on Non Dosing Days 31, 45, 73, 87, 101 and 115 (For Cohorts 5 to 9 only)

All study visits are to be scheduled relative to the Baseline/Day 1 visit. Study visits on Day 31, Day 45, Day 73, Day 87, Day 101 and Day 115 Day are to be completed within ± 1 day of the protocol specified visit date. The following procedures will be performed:

- 6.4.5.1. Review of AEs and changes in concomitant medication
- 6.4.5.2. Symptom-directed physical examination as needed
- 6.4.5.3. Urine collection for urinalysis (**Days 73, 87, 101 and 115 only**)
- 6.4.5.4. Blood sample collection for the following laboratory analyses:
 - 6.4.5.4.1. Chemistry profile: alkaline phosphatase, AST, ALT, total bilirubin, direct and indirect bilirubin, total protein, albumin, CPK, bicarbonate, BUN, calcium, chloride, creatinine, glucose, phosphorus, magnesium, potassium, sodium, uric acid (**Days 73, 87, 101 and 115 only**)
 - 6.4.5.4.2. Hematology profile: complete blood count (CBC) with differential and platelet count (**Days 73, 87, 101 and 115 only**)
 - 6.4.5.4.3. Plasma HIV-1 RNA (TaqMan[®] v2.0)
 - 6.4.5.4.4. Serum for cytokine/soluble biomarker studies (**Day 45**, only if the SEC approves the dose escalation to 12 mg in Cohort 6 starting from Dose 4)
 - 6.4.5.4.5. Whole blood ISG mRNA panel (**Day 45**, only if the SEC approves the dose escalation to 12 mg in Cohort 6 starting from Dose 4)

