to 6, CCI of their assigned study treatment administered once every other week. For all subjects in Cohort 6, Dose 4 (Day 43) will occur after SEC review has been completed. If dose escalation is approved by the SEC, subjects in Cohort 6 will receive 12 mg of VES or placebo from Doses 4 to 10; if dose escalation is not approved by the SEC, subjects will continue receiving 10 mg of VES or placebo from Doses 4 to 10.

For Cohorts 1 to 3, dosing visits will occur at Day 1, Day 15, Day 29, Day 43, Day 57, and Day 71. For Cohorts 4 to 9, dosing visits will occur at Day 1, Day 15, Day 29, Day 43, Day 57, Day 71, Day 85, Day 99, Day 113 and Day 127. CCI

For Cohorts 1 to 4, subjects will fast for at least 2 hours before dosing. For Cohorts 5 to 8, subjects will fast overnight (at least 8 hours) before dosing. CCI

The Investigator will verify the subject's continued eligibility for dosing at post-Baseline dosing visits, including the absence of DLTs and (for females of childbearing potential) a negative urine pregnancy test, prior to dosing. All doses will be directly administered by blinded site staff.

Laboratory analyses (hematology, serum chemistry, and urinalysis) will be performed weekly for Cohorts 1 to 3. For Cohorts 4 to 9, these labs will be collected on dosing days, seven days post dose (starting from Dose 4), at end of study, and early study drug discontinuation (ESDD). For Cohorts 6, CCI these labs will also be collected on Day 2 and two days post dose (starting from Dose 5). CCI

Urine pregnancy test (for females of childbearing potential) will be performed prior to each dose. Vital signs (blood pressure, pulse, respiration rate and temperature) will be measured at all dosing visits.

Plasma HIV-1 RNA will be measured at every visit except Pre-Baseline (Day -13). Cell-associated HIV-1 RNA/DNA (CAVR/CAVD), and plasma HIV-1 RNA by SCA will be collected immediately before and two days post Doses 1, 4, 6 and at end of the study (Cohort 1 to 3); immediately before and two days post Doses 1, 5, 10 and at end of the study (Cohorts 4 to 9). CCI

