	Day 48	Day 13	Baseline/Day	Day 2	Day 3	Day 8	Day 15	Day 22	Day 29	Day 31	Day 36	Day 43	Day 45	Day 50	Day 57	Day 58	Day 59	Day 64	Day 71	Day 73	Day 78	Day 85	Day 87	Day 92	Day 99	Day 101	Day 106	Day 113	Day 115	Day 120	Day 127	Day 128	Day 129	Day 134	Day 157		
Plasma HIV-1 RNA	X		X	X	X	X	X	X	X	X	X	X	X	X	X	X	X	X	X	X	X	X	X	X	X	X	X	X	X	X	X	X	X	X	X	X	
CD4+ cell count, CD8+ cell count, CD4/CD8 ratio and CD4 %	X		X				X		X			X		X	X			X	X			X		X		X		X		X				X	X	X	
Chemistry profile	X		X	X B			X		X			X		X	X		X B	X	X	X B	X	X	X B	X	X	X B	X	X	X B	X	X B	X	X	X B	X	X	X
Hematology profile	X		X	X B			X		X			X		X	X		X B	X	X	X B	X	X	X B	X	X	X B	X	X	X B	X	X B	X	X	X B	X	X	X
HBV/HCV Serology	X																																				
Estimated GFR	X		X																																X	X	
Urinalysis	X		X	X B			X		X			X		X	X		X B	X	X	X B	X	X	X B	X	X	X B	X	X	X B	X	X B	X	X	X B	X	X	X
Urine Pregnancy Test j			X				X		X			X		X					X			X			X		X					X			X	X	
Serum Pregnancy Test j	X																																				
Plasma GS-9620 Intensive PK k			X		X							X n	X n																								
Plasma ART PK p	X								X					X								X				X											
TLR7 genotyping		X																																			
Serum for cytokine/soluble biomarker studies			X o	X	X							X n	X n	X n	X o	X	X	X													X o	X	X	X		X	

Study Procedure a	Screen	PreBaseline	Dose 1	Day 1 Post Dose	Day 2 Post Dose	Day 7 Post Dose	Dose 2	Day 7 Post Dose	Dose 3	Day 2 Post Dose	Day Post Dose	Dose 4	Day 2 Post Dose	Day 7 Post Dose	Dose 5	Day 1 Post Dose	Day 2 Post Dose	Day 7 Post Dose	Dose 6	Day 2 Post Dose	Day 7 Post Dose	Dose 7	Day 2 Post Dose	Day 7 Post Dose	Dose 8	Day 2 Post Dose	Day 7 Post Dose	Dose 9	Day 2 Post Dose	Day 7 Post Dose	Dose 10	Day 1 Post Dose	Day 2 Post Dose	Day 7 Post Dose	End of Study	ESDD	
	Post-Baseline study visits e																																				

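### For Cohorts 5 to 9, Protocol 6.4.3 omits the Day 106 safety panel (seven days after Dose 8) that the synopsis, SAP 1.2 and the SAP schedule table call for

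*Protocol*

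**What the plan says.** The synopsis (On-Study Procedures, Safety) sets one rule for Cohorts 4 to 9. Of hematology, chemistry and urinalysis it says that "these labs will be collected on dosing days, seven days post dose (starting from Dose 4), at end of study, and ESDD". SAP 1.2 repeats it: "these labs will be collected on dosing days, seven days post dose (starting from Dose 4), at end of study". Neither makes an exception for Dose 8.

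The visit lists in the synopsis place Day 106 seven days after Dose 8: "Day 99 (Dose 8), Day 106" for Cohort 4 and "Day 99 (Dose 8), Day 101, Day 106" for Cohorts 5 to 9.

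Protocol Section 6 says that procedures are tabulated in Appendix 2 "and described in the text that follows". In that text, Section 6.4.3 names Day 106 as a visit in its heading and in its window sentence. Its urinalysis, chemistry and hematology items (6.4.3.3, 6.4.3.4.1, 6.4.3.4.2) are then limited to "Days 50, 64, 78, 92, 120 and 134 only". The CD4 and CD8 items (6.4.3.4.4, 6.4.3.4.4.1) give the same six days. On Day 106 there remain adverse event and medication review, symptom-directed examination and plasma HIV-1 RNA.

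In the SAP Appendix 2 table for Cohorts 5 to 9, the row "Chemistry profile" and the hematology and urinalysis rows carry a mark on Day 106.

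**The concern.** The general rule and the detailed instruction disagree on one visit, and no reason is given for treating Dose 8 differently. A site working from 6.4.3 draws no safety panel on Day 106. A site working from the synopsis draws one.

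Safety monitoring late in dosing is at stake. Section 7.6.1 requires the investigator to verify, before each dose, that no dose-limiting toxicity (DLT) is present. Two of the criteria rest on the omitted labs: ALT elevation, and a confirmed, clinically significant, drug-related laboratory abnormality of Grade 3 or higher. Section 7.6.2 allows three calendar days from receipt of results for confirmation by repeat testing. An abnormality found on Day 106 could be confirmed before Dose 9 on Day 113. One first seen in the Day 113 sample may not be.

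**Working it through.** **Inputs.** Dosing days for Cohorts 4 to 9 are 1, 15, 29, 43, 57, 71, 85, 99, 113 and 127 (synopsis, Dosing). The rule comes from the synopsis and SAP 1.2. The listed lab days come from 6.4.3.

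**1. Days required by the rule.** Dose k falls on Day 1 + 14(k − 1), and the panel falls seven days later, for k = 4 to 10.

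| Dose | Dosing day | + 7 | In 6.4.3 |
|---|---|---|---|
| 4 | 43 | 50 | yes |
| 5 | 57 | 64 | yes |
| 6 | 71 | 78 | yes |
| 7 | 85 | 92 | yes |
| 8 | 99 | 106 | **no** |
| 9 | 113 | 120 | yes |
| 10 | 127 | 134 | yes |

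The rule gives 7 days and 6.4.3 lists 6. Exactly one is missing and none is extra.

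**2. Which side the schedule tables take.**

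- *Cohorts 5 to 9, SAP Appendix 2.* The chemistry row has 37 cells for 36 columns, so its alignment has to be shown. Counted from the left, the footnoted marks fall on Days 2, 59, 73, 87, 101 and 115. These are the Day 2 and two-day visits with labs in 6.4.1, 6.4.2 and 6.4.5. The row is therefore aligned through that stretch, and the surplus cell comes only after Day 120. Cell 26 (Day 101) is footnoted, and cell 27 (Day 106) and cell 28 (Day 113) hold plain marks. Hematology and urinalysis show the same pattern. The CD4/CD8 row has 36 cells but leaves dosing Days 99 and 127 blank, although 6.4.4 requires the count there, so it is not evidence either way. The matching rows of the protocol's own table are not in the available text.
- *Cohort 4.* The protocol chemistry row has 30 cells for 30 columns, and cell 22 (Day 106) is blank. The SAP chemistry, hematology and CD4 rows have lost one blank cell, but counted from the right they also leave Day 106 blank.

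So 6.4.3 is the outlier for Cohorts 5 to 9. For Cohort 4 the outlier is the summary sentence.

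**3. Longest interval between panels, Dose 8 to Dose 9.**

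- By the rule: Day 99 to 106 to 113, so 7 days.
- Cohort 5 by 6.4.3: 113 − 99 = 14 days.
- Cohort 6 by 6.4.3: Day 101 labs remain, so 113 − 101 = 12 days.

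The Day 101 labs come from 6.4.5 ("Days 73, 87, 101 and 115 only"). That section is headed for Cohorts 5 to 9, but the synopsis gives two-day labs only to Cohort 6 and redacted cohorts, so Cohort 5 is not credited with them. If the 6.4.5 heading were taken literally, Cohort 5 would also be at 12 days.

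**4. Panels affected.** 2 cohorts × 8 subjects = 16, of which 2 × 6 = 12 are active and 2 × 2 = 4 placebo.

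**The case against.** The strongest reply is that the omission is deliberate. All five items in 6.4.3 drop the same day, and the Cohort 4 tables in both documents agree with them. For Cohort 4 this stands. A reader might infer that 6.4.3 is wrong for every cohort from 4 on and count 3 × 8 = 24 lost panels. The documents do not support that: in Cohort 4 the detailed sources agree, and Protocol 1.4 reports that the cohort has already received its 10 doses. For Cohorts 5 to 9 the reply is weaker, because the SAP table marks the day. Blood volume is a poor explanation, since urinalysis was dropped too.

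A second reply is that the gap is unremarkable. The same rule accepts 14 days between panels after Doses 1 to 3 in Cohort 5 (13, 14 and 14 in Cohort 6) and 23 days from Day 134 to Day 157. Day 106 keeps adverse event review and HIV-1 RNA, and labs return on Day 113. This stands and keeps the point small. It does not explain why the weekly schedule that starts at Dose 4 should lapse once, at Dose 8.

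A reader might also infer that Day 106 results would be lost from the by-visit tables as unscheduled data under SAP 3.8.2. They would not be. Day 106 is a scheduled visit and the SAP analyzes by nominal visit. Even unscheduled results count toward the maximum postbaseline toxicity grade.

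**Conclusion.** The inconsistency is real for Cohorts 5 to 9, and the fault lies in 6.4.3. Followed literally, it costs one seven-day panel per subject (6 instead of 7). It lengthens the gap before the Dose 9 toxicity check from 7 days to 14 in Cohort 5 and 12 in Cohort 6. At most 16 panels in Cohorts 5 and 6 are concerned. No efficacy endpoint is touched, and the planned laboratory summaries are descriptive.

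This rests on two readings: that the SAP table for Cohorts 5 to 9 is aligned at Day 106, which its footnoted marks support, and that the synopsis governs who has two-day labs. How many subjects can still benefit is unknown. At the 30 April 2018 data cut in Protocol 1.4, all Cohort 5 subjects had completed five doses and three had completed six. SAP 2.1.1 describes the safety committee reviews, including Cohort 6, as already performed, so few or none may still be before Day 106.

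**What to change.** For Cohorts 5 to 9 subjects not yet past the visit, add Day 106 to 6.4.3.3, 6.4.3.4.1 and 6.4.3.4.2. Add it also to 6.4.3.4.4 and 6.4.3.4.4.1, because the synopsis counts CD4 and CD8 in the hematology panel. Restrict the additions to Cohorts 5 to 9.

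For Cohort 4, leave 6.4.3 and the tables alone and correct the synopsis and SAP 1.2 sentence to state the Dose 8 exception. If Day 106 was left out on purpose in the later cohorts too, give the reason and correct the synopsis, SAP 1.2 and the SAP table instead.

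The cost is one day number in five items, one corrected sentence in each of two documents, and one extra panel per remaining subject at a visit that already draws blood. The added tubes must fit the cap of 473 mL per 56 days. The documents give no tube volumes, so this needs checking first. No extra report table is needed: the number of subjects per visit and treatment planned in SAP 3 and 7.2.1 will show how many Day 106 panels were drawn.

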6.4.4.9. In-Clinic Dosing

6.4.5. Treatment Assessments on Non Dosing Days 31, 45, 73, 87, 101 and 115 (For Cohorts 5 to 9 only)

All study visits are to be scheduled relative to the Baseline/Day 1 visit. Study visits on Day 31, Day 45, Day 73, Day 87, Day 101 and Day 115 Day are to be completed within ± 1 day of the protocol specified visit date. The following procedures will be performed:

- 6.4.5.1. Review of AEs and changes in concomitant medication
- 6.4.5.2. Symptom-directed physical examination as needed
- 6.4.5.3. Urine collection for urinalysis (**Days 73, 87, 101 and 115 only**)
- 6.4.5.4. Blood sample collection for the following laboratory analyses:
 - 6.4.5.4.1. Chemistry profile: alkaline phosphatase, AST, ALT, total bilirubin, direct and indirect bilirubin, total protein, albumin, CPK, bicarbonate, BUN, calcium, chloride, creatinine, glucose, phosphorus, magnesium, potassium, sodium, uric acid (**Days 73, 87, 101 and 115 only**)
 - 6.4.5.4.2. Hematology profile: complete blood count (CBC) with differential and platelet count (**Days 73, 87, 101 and 115 only**)
 - 6.4.5.4.3. Plasma HIV-1 RNA (TaqMan[®] v2.0)
 - 6.4.5.4.4. Serum for cytokine/soluble biomarker studies (**Day 45**, only if the SEC approves the dose escalation to 12 mg in Cohort 6 starting from Dose 4)
 - 6.4.5.4.5. Whole blood ISG mRNA panel (**Day 45**, only if the SEC approves the dose escalation to 12 mg in Cohort 6 starting from Dose 4)

